6.5 Immunochemistry

Serum- and 24h urine- protein electrophoresis and immunofixation (IFE)

For measurement of M-protein at entry and to confirm CR. The samples of IgG – myeloma patients will be frozen for later analyses. Helsinki University Hospital

Helsinki University Hospital Comprehensive Cancer Center Hematology
Clinical study protocol NMSG#24/15

laboratory is developing the method for analysing the IFE samples of IgG patients who have treated with elotuzumab. Serum samples will be stored before treatment, at best response and at relapse from all patients.

Quantification of serum- or urine M-component always when response is assessed

Serum free light chain (S-FLC) assay always when response is assessed

6.6 Bone marrow assessment

Bone marrow samples at entry for multiparameter flow cytometry (MFC) (if it has not taken at diagnosis) and if VGPR/CR has been achieved and annually if response has been maintained

Bone marrow samples at entry for FISH analysis to investigate del17p and screening of translocations 4;14, 14;16 and 14;20, +1q, except the patient already has had these aberrations.

6.7 Specific additional investigations

- Bone imaging: Low-dose whole body CT, MRI, or x-ray according to local MM guidelines: at entry and if clinically indicated
- Electrocardiogram from all patients at entry and at the end of study, and if clinically indicated
- Cardiological investigations, echo at base line
- Spirometry and diffusion capacity, if clinically needed

Patients are asked to fill quality of life questionnaire at inclusion, on day 1 and 15 of cycles 1 – 8 thereafter on day 1 of each cycle and in the end of study.

7. SAFETY ASSESSMENT

Study investigators must follow the study protocol treatment and follow the dose reduction and adjustment guidelines in every study patient. Exceptional issues should be discussed with principal investigator. Adverse event will be documented if observed, mentioned during open questioning, or when spontaneously reported.

7.1 ADVERSE EVENT REPORTING

All Serious Adverse Events (SAEs) that occur following the subject's written consent to participate in the study through 60 days of discontinuation of dosing must be reported.

Intensity for each SAE, including any lab abnormalities, will be determined by using the NCI CTCAE version 4.0 (v4.03. June 14, 2010), as a guideline, whenever possible. The criteria are available online at <http://ctep.cancer.gov/reporting/ctc.html>

In this multicenter study all adverse events will be reported centrally using the accepted SAE and SUSAR report forms and CIOMS form (Appendix 7) via principal investigator [name]/Helsinki University Hospital [contact]

Adverse Events

- An Adverse Event [AE] is defined as any new untoward medical occurrence or worsening of a pre-existing medical condition in a patient or clinical investigation subject administered an investigational (medicinal) product and that does not necessarily have a causal relationship with this treatment. An AE can therefore be any unfavorable and unintended sign (including an abnormal laboratory finding, for example), symptom, or disease temporally associated with the use of investigational product, whether or not considered related to the investigational product.
- The causal relationship to study drug is determined by a physician and should be used to assess all adverse events (AEs). The causal relationship can be one of the following:
 - Related: There is a reasonable causal relationship between study drug administration and the AE.

Helsinki University Hospital Comprehensive Cancer Center Hematology
Clinical study protocol NMSG#24/15

- Not Related: There is not a reasonable causal relationship between study drug administration and the AE.
- The term “reasonable causal relationship” means there is evidence to suggest a causal relationship.
- Adverse events can be spontaneously reported or elicited during open-ended questioning, examination, or evaluation of a subject. (In order to prevent reporting bias, subjects should not be questioned regarding the specific occurrence of one or more adverse events).

7.2 Serious Adverse Events

A **Serious Adverse Event (SAE)** is any untoward medical occurrence at any dose that:

- results in death
- is life-threatening (defined as an event in which the subject was at risk of death at the time of the event; it does not refer to an event which hypothetically might have caused death if it were more severe)
- requires inpatient hospitalization or causes prolongation of existing hospitalization
- results in persistent or significant disability/incapacity
- is a congenital anomaly/birth defect
- is an important medical event, defined as a medical event that may not be immediately life-threatening or result in death or hospitalization but, based on appropriate medical and scientific judgment, may jeopardize the subject or may require intervention (eg, medical, surgical) to prevent one of the other serious outcomes listed above. Examples of such events include but are not limited to intensive treatment in an emergency department or at home for allergic bronchospasm; blood dyscrasias or convulsions that do not result in hospitalization.

Helsinki University Hospital Comprehensive Cancer Center Hematology
Clinical study protocol NMSG#24/15

- Potential drug-induced liver injury (DILI) is also considered an important medical event--see the DILI section below for a definition of a potential DILI event.

Suspected transmission of an infectious agent (eg, pathogenic or non-pathogenic) via the study drug is an SAE.

Although pregnancy, overdose, cancer and potential drug induced liver injury (DILI) are not always serious by regulatory definition, these events must be handled as SAEs.

The following hospitalizations are not considered SAEs:

- Elective surgery planned before signing consent
- Admissions as per protocol for a planned medical/surgical procedure
- Routine health assessment requiring admission for baseline/trending of health status (eg, routine colonoscopy)
- Medical/surgical admission other than remedying ill health state that was planned before study entry. Appropriate documentation is required in these cases
- Admission encountered for another life circumstance that carries no bearing on health status and requires no medical/surgical intervention (eg, lack of housing, economic inadequacy, caregiver respite, family circumstances, administrative reason)

Serious Adverse Event Collecting and Reporting

Following the subject's written consent to participate in the study, all SAEs, whether related or not related to study drug, must be collected, including those thought to be associated with protocol-specified procedures. All SAEs must be collected that occur during the screening period and within 60 days of discontinuing dosing. If applicable, SAEs must be collected that relate to any later protocol-specific procedure (such as follow-up skin biopsy).

The investigator should report any SAE occurring after these time periods that is believed to be related to study drug or protocol-specified procedure.

An SAE report should be completed for any event where doubt exists regarding its status of seriousness.

Helsinki University Hospital Comprehensive Cancer Center Hematology
Clinical study protocol NMSG#24/15

If the investigator believes that an SAE is not related to study drug, but is potentially related to the conditions of the study (such as withdrawal of previous therapy, or a complication of a study procedure), the relationship should be specified in the narrative section of the SAE Report Form (CIOMS form).

SAEs, whether related or unrelated to the study drug, and pregnancies must be reported within 24 hours, SAEs must be recorded on the SAE Report Form; Pregnancies on a Pregnancy Surveillance Form (Appendix 8)

If only limited information is initially available, follow-up reports are required. (Note: Follow-up SAE reports should include the same investigator term(s) initially reported.)

If an ongoing SAE changes in its intensity or relationship to study drug or if new information becomes available, a follow-up SAE report should be sent within 24 hours using the same procedure used for transmitting the initial SAE report.

All SAEs should be followed to resolution or stabilization.

7.3 Health Authority Reporting (SUSAR reporting, Annual Safety reporting, any significant new observations reporting)

Investigators must adhere to local Health Authority Reporting Requirements.

The SUSARs will be reported to companies and to National Regulatory Authorities by the Sponsor-Investigator: Finnish Medicines Agency (FIMEA), Eudravigilance Database, and the appropriate Swedish Ethics Committee with CIOMS Form I.(<http://www.cioms.ch/index.php/cioms-form-i>).

Helsinki University Hospital Comprehensive Cancer Center Hematology
Clinical study protocol NMSG#24/15

Adverse drug reactions that are Serious, Unexpected, and at least Possibly Related to the drug (Suspected Unexpected Serious Adverse Reaction, SUSAR) and that have not previously been reported in the Investigators' Brochure, or reference safety information document will be reported promptly to the health authority in writing by the Principal Investigator.

A clear description of the suspected reaction should be provided along with an assessment as to whether the event is drug or disease related. The Principal Investigator shall notify the health authorities by fax or email of any unexpected fatal or life threatening experience associated with the use of the drugs as soon as possible but no later than 7 calendar days after initial receipt of the information. Other serious SUSARs should be reported within 15 days.

SAE's will be reported 3 months after last study drug dose but SUSAR's will be reported 1 year after last study drug dose.

The annual safety report (list of all suspected serious adverse reactions which have occurred during the period of time in question) will be provided to companies, Finnish Medicines Agency, Medical Products Agency (MPA) and appropriate Finnish and Swedish Ethics Committees by the Investigator-Sponsor. In Finland the annual safety report will be provided together with a brief report of the safety of persons participating in the clinical trial (signed by the person responsible for the trial).

The sponsor must without delay inform the investigators, Fimea, MPA and appropriate Ethics Committee of any significant new observations relating to the safety of the investigational medicinal product.

BMS wishes that Sponsor provides SUSARs and Annual Safety Reports, submitted to the applicable Regulatory Authorities and Ethics Committees, also to BMS either by email to [contact] or by fax to Central Facsimile Station at [contact]. BMS wishes to receive SUSARs and

Helsinki University Hospital Comprehensive Cancer Center Hematology
Clinical study protocol NMSG#24/15
Annual Safety Reports within twenty four (24) hours of Sponsor submitting the report to the applicable Regulatory Authority and Ethics Committee.

Amgen SUSAR reporting:

When Sponsor receives a SUSAR, it shall transmit the final CIOMS report of that event to Amgen within **twenty four (24) hours** of submitting that report to the applicable regulatory authority

Amgen Global Safety:

US Toll Free [contact]

For countries where the U.S. toll-free # cannot be used: [contact]

Email (Only for sponsors with a secure email connection with Amgen): [contact]

Non-Serious Adverse Events

A non-serious adverse event is an AE not classified as serious. Non-Serious adverse events \geq grade 2 will be collected and reported via annual safety reports and final study reports. These AEs will be collected until 30 days after the last dose of study treatment.

Laboratory Test Abnormalities

The following laboratory abnormalities should be captured and reported as appropriate:

- Any laboratory test result that is clinically significant or meets the definition of an SAE
- Any laboratory test result abnormality that required the subject to have study drug discontinued or interrupted
- Any laboratory test result abnormality that required the subject to receive specific corrective therapy.

Laboratory test abnormalities are provided to AMGEN via annual safety reports (if applicable), and interim or final study reports.

7.4 PREGNANCY

If, following initiation of the investigational product, it is subsequently discovered that a study subject is pregnant or may have been pregnant at the time of investigational product exposure, including during at least 6 half-lives after product administration, the investigational product will be permanently

Helsinki University Hospital Comprehensive Cancer Center Hematology
Clinical study protocol NMSG#24/15
discontinued in an appropriate manner (eg, dose tapering if necessary for subject safety).

The investigator must immediately notify the Amgen safety of this event via the Pregnancy Surveillance Form within 24 hours and in accordance with SAE reporting procedures.

Follow-up information regarding the course of the pregnancy, including perinatal and neonatal outcome and, where applicable, offspring information must be reported on a Pregnancy Surveillance Form.

Any pregnancy that occurs in a female partner of a male study participant should be reported.. Information on this pregnancy may also be collected on the Pregnancy Surveillance Form.

Protocol-required procedures for study discontinuation and follow-up must be performed on the subject unless contraindicated by pregnancy (eg, x-ray studies). Other appropriate pregnancy follow-up procedures should be considered if indicated.

7.5 OVERDOSE

Definition of overdose in this study is any accidental overdose which is overdose based on calculations of body surface are for carfilzomib or mg/kg for elotuzumab, or dose of dexamethasone which is above normal weekly dose except doses of glucocorticoid used for treat of adverse events and will be reported properly.

An overdose is defined as the accidental or intentional administration of any dose of a product that is considered both excessive and medically important. All occurrences of overdose must be reported as SAEs.

7.6 Potential Drug-Induced Liver Injury (DILI)

Wherever possible, timely confirmation of initial liver-related laboratory abnormalities should occur prior to the reporting of a potential DILI event.

Helsinki University Hospital Comprehensive Cancer Center Hematology
Clinical study protocol NMSG#24/15

All occurrences of potential DILIs meeting the defined criteria must be reported as SAEs.

Potential drug induced liver injury is defined as

1. AT (ALT or AST) elevation > 3 times upper limit of normal (ULN), AND

Total bilirubin > 2 times ULN, without initial findings of cholestasis (elevated serum alkaline phosphatase), AND

2) No other immediately apparent possible causes of AT elevation and hyperbilirubinemia, including, but not limited to, viral hepatitis, pre-existing chronic or acute liver disease, or the administration of other drug(s) known to be hepatotoxic.

7.7 Other Safety Considerations

Any significant worsening noted during interim or final physical examinations, electrocardiograms, x-rays, and any other potential safety assessments, whether or not these procedures are required by the protocol, should also be recorded as a nonserious or serious adverse event, as appropriate, and reported accordingly.

8. DATA MONITORING COMMITTEE

The multicenter electronic Case Report Form System, where all study data will be collected and reported, is led via Principal Investigator in Helsinki University Hospital Finland. The filled data will be followed during annual meetings of Nordic Myeloma Study Group and Finnish Myeloma Group.

Independent staff of Research Units of University Hospitals in Sweden and Finland will monitor this study at level 2. Inclusion criteria, endpoints and all key test results according to the assessment schedule will be monitored to assure data quality. The investigator is required to permit direct access to the facilities where the study took place, source documents, CRFs and applicable supporting records of subject participation for audits and inspections by Ethics Committees and

Helsinki University Hospital Comprehensive Cancer Center Hematology
Clinical study protocol NMSG#24/15

National Medicines Agency. The investigator should make every effort to be available for the audits and/or inspections

The Finnish Association of Hematology will act as an external Safety Board in this study, and all adverse events will be informed and discussed every 6-8 months. Physicians who are involved in this study are not participating in the Board.

8.1 DATA AND DOCUMENTS HANDLING

Documents which are essential for evaluation of conduct of the study and the quality of data will be filed in such a manner that they are protected from accidental loss. The sponsor-investigator will file all national essential regulatory documents relevant to the overall conduct of the trial. Local investigators will file all essential documents relevant to the conduct of the trial on site. Essential documents will be retained for 15 years after the end of the trial and the final presentation of the study. Source documents and medical records of patients should be retained for 15 years after the end of the trial. After this time these documents will be handled by the site's guidelines regarding medical records.

8.2 AMENDMENTS

Any amendments to this protocol that seems appropriate, as the study proceeds (regarding safety, efficacy, conduction or scientific value of the study) will be agreed upon the coordinating and/or principal investigator and investigator-sponsor. Amendments will be submitted to the Ethics Committee and the regulatory authority for written approval before the implementation of the amended version. Companies will be informed about possible amendments before sending to Ethical Committee.

9. STATISTICAL CONSIDERATIONS

This is a phase 2 study with an experimental new combination for treatment of relapsed or progressive multiple myeloma. The number of patients in explorative phase 2 trials is usually from 20 to 60 patients. No formal statistical calculations or sample size determination have been performed for this pilot trial. The expected overall response rate is 70 %. With N=40 the CI95% for the expected ORR is 53-83%. The selected sample size is therefore considered adequate to rule out ORRs lower than 53%, when then observed ORR is in line with the assumption of 70 %. If the combination will fill the expectations listed in section 9.2 below the study might be expanded to include additional number of patients based on statistical power calculations.

9.1 ENDPOINT DEFINITIONS

Primary endpoint of this study is overall response rate

Secondary endpoints are

- Complete remission (CR) rate
- Quality of response (proportion of MRD negativity in patients with at least VGPR)
- Duration of responses including MRD negativity
- Progression-free survival (PFS)
- Time to next treatment (TTNT)
- Safety (Adverse events)

Minimal residual disease (MRD) will be assessed by 8-colour EuroFlow multiparameter flow cytometry if at least VGPR has been achieved.

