6.1	Medical previous history	54
6.2	Physical examinations	54
6.3	Hematology	55
6.4	Blood chemistry	55
6.5	Immunochemistry	55
6.6	Bone marrow assessment	56
6.7	Specific additional investigations	56
7	SAFETY ASSESSMENT	56
7.1	Adverse Events Reporting	57
7.2	Serious Adverse Events	58
7.3	SUSAR reporting	60
7.4	Pregnancy	62
7.5	Overdose	63
7.6	Potential Drug-Induced Liver Injury (DILI)	63
7.7	Other Safety Considerations	64
8	DATA MONITORING COMMITTEE	65
8.1	Data and documents handling	65
8.2	Amendments	65
9	STATISTICAL CONSIDERATIONS	65
9.1	Endpoint Definitions	66
9.2	Statistical and Efficacy Analyses	66
9.3.	Demographics and Baseline Characteristics	67
10	STUDY MANAGEMENT	68
10.1	Compliance with the Protocol	68
10.2	Publication	68
10.3	Destruction of investigational products	68
	APPENDIX 1 ECOG SCALE	69
	APPENDIX 2 COCKCROFT-GAULT EQUATION	69
	APPENDIX 3 NYHA CLASSIFICATION	70
	APPENDIX 4 ISS STAGE	70
	APPENDIX 5 IMWG CRITERIA	71
	APPENDIX 6 ELOTUZUMAB ADMINISTRATION GUIDELINES	74
	APPENDIX 7 CIOMS FORM	77
	REFERENCES	78

Principal Investigator signature page

Signature of Investigator

Printed name of Investigator

Date

LOCAL INVESTIGATOR SIGNATURE

Local site name: _____

Local Investigator: _____
Signature of Investigator

Printed name of Investigator

Date

By my signature, I agree to personally supervise the conduct of this study and to ensure its conduct in compliance with the protocol, informed consent, IRB/EC procedures, the Declaration of Helsinki, ICH Good Clinical Practices guideline, the EU directive Good Clinical Practice, and local regulations governing the conduct of clinical studies.

Study Title: Phase 2 study carfilzomib + elotuzumab + dexamethasone for relapsed or progressed multiple myeloma patients after 1-3 prior treatment lines

Phase: Phase 2

Number of Patients: 40

Study Objective: To investigate the safety and feasibility of carfilzomib + elotuzumab + dexamethasone combination and initial efficacy in relapsed or progressed multiple myeloma patients

Study Endpoints

Primary

- Overall response rate (ORR) with carfilzomib + elotuzumab + dexamethasone

Secondary

Complete response rate (CR)

- Quality of response (proportion of minimal residual disease (MRD) negativity in patients with at least VGPR response)
- Duration of responses
- Progression-free survival (PFS)
- Time to next treatment (TTNT)
- Safety (Adverse events)

Overview of Study Design:

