This Nordic Myeloma Study Group study is a phase 2 study for advanced MM patients below 75 years of age. The main aim of this study is to assess the ORR with a new drug combination, carfilzomib + elotuzumab + dexamethasone (CAR-ELO-Dex). Even if this is not a randomized study rough comparisons can be done with earlier reports of different regimens in the same clinical situation. In addition, safety assessment is of critical importance for a new regimen. A modern concept is to study the depth of CR responses with a sensitive multiparameter flow cytometry (MFC) method for MRD assessment – an endpoint that is mostly lacking in previous studies for this patient population. We assume that treatment with this new combination of CAR + ELO + Dex will produce at least as good responses as the most efficient regimens so far used in this clinical situation, and there will be a substantial proportion of CR responses with MRD-negativity which can be regarded as an indicator of high-level treatment efficacy and which gives a good basis for comparisons of treatment efficacy between different study regimens in future.

The target population of the study is the patients who have relapsed or progressed after 1 to 3 prior treatment lines in which PI (bortezomib and/or ixazomib) and/or lenalidomide have

Helsinki University Hospital Comprehensive Cancer Center Hematology
Clinical study protocol NMSG#24/15

been included. The primary endpoint is overall response rate (ORR) while the secondary endpoints include complete remission (CR), duration of response, assessment of the depth (quality) of CR with MRD measurement by flow cytometry, estimation of PFS and time to next treatment, and evaluation of adverse events and safety.

The cycle length is 28 days.

The ELO dose is 10 mg/kg in all cycles.

CAR dose is initially (Cycle 1, day 1) 20 mg/m² weekly after which it will be increased to 56 mg/m² weekly in the first 5 patients in the first two cycles. If no safety problems occur the dose is increased to 70 mg/m² weekly for the rest of the study, and the patients after the first 5 patients will receive this dose right after the initial weekly dose of 20 mg/m²

Dexamethasone dose is 40 mg weekly throughout the study.

Drug administration schedule:

Cycles 1-2

CAR and ELO are administrated at weekly intervals on cycle days 1, 8 and 15.

Dexamethasone will be given on days 1, 8, 15 and 22.

Cycles 3-8

CAR will be administered similarly as in cycles 1-2.

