We may assume that combining elotuzumab and carfilzomib is a feasible study protocol design and may well produce higher CR rates than elotuzumab plus lenalidomide. MRD status has usually not been used in the response analyses, and this aspect will strengthen the value of efficacy assessment of CAR+ELO combination and may allow comparisons to other regimens in future.

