9.2 STATISTICAL AND EFFICACY ANALYSES

Statistical analyses will be performed on intention-to-treat and on per-protocol-treated principle. Patients who have been included in the study but been withdrawn before any study drug administration are not included in analyses. Safety and efficacy analyses will be done for all patients who have received at least a single dose of study drug. Any spurious data will be abandoned. Missing

Helsinki University Hospital Comprehensive Cancer Center Hematology
Clinical study protocol NMSG#24/15

data will be handling as missing data not with replacing it with a median parameter number.

Efficacy analyses will be done using International Myeloma Working Group response criteria (Appendix 5). Response will be assessed before each cycle. Progression will be assessed using IMWG criteria for progressive disease.

For classification the adverse events NCI CTCAE version 4.0 will be used. Threshold for safety of this CAR-ELO-Dex combination is considered to be less than 70% of grade ≥ 3 non-hematological adverse events.

Efficacy, safety and QoL analysis will be performed when last patient in has been treated for two years in the study. Kaplan-Meier method will be used to estimate the time to event analyses. The PFS, TTNT and duration of response will be calculated from the start of the first dose of study drug combination.

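### The MRD endpoint is defined only among patients reaching at least VGPR, a poor headline measure for the between-regimen comparisons the protocol has in mind

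*Protocol*

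**What the plan says.** Section 9.1 lists the secondary endpoint as "Quality of response (proportion of MRD negativity in patients with at least VGPR". The synopsis endpoint list agrees: "Quality of response (proportion of minimal residual disease (MRD) negativity in patients with at least VGPR response". Testing follows the same rule in section 9.1: "Minimal residual disease (MRD) will be assessed by 8-colour EuroFlow multiparameter flow cytometry if at least VGPR has been achieved".

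On the purpose of the measure, the Overview of Study Design in the synopsis says that a substantial share of complete responses with MRD negativity "gives a good basis for comparisons of treatment efficacy between different study regimens in future". The end of section 1.2.2 says that MRD status "may allow comparisons to other regimens in future". The Overview also describes the secondary endpoint more narrowly, as "assessment of the depth (quality) of CR with MRD measurement by flow cytometry".

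Two sentences in section 9.2 bear on the denominator. One sets the general analysis population: "Safety and efficacy analyses will be done for all patients who have received at least a single dose of study drug". The other says that missing "data will be handling as missing data not with replacing it with a median parameter number". Neither mentions MRD, and nothing in the protocol says how a patient without an MRD result is counted.

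**The concern.** A proportion whose denominator is a treatment outcome answers a conditional question: among those who responded deeply, how many also cleared MRD? That is a fair descriptive question about depth of response. It does not tell the reader how often the regimen produces MRD negativity in the patients who start it, which is what a comparison of regimens needs.

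The conditional figure rises if more patients become MRD-negative. It also rises if fewer patients reach VGPR while the MRD-negative count holds steady or falls less steeply. Two regimens with different VGPR rates therefore cannot safely be ranked on it. This matters because the protocol singles out MRD as an efficacy measure largely absent from earlier studies in this population and expects it to be used in later comparisons. The percentage named in section 9.1 is the one most likely to be carried forward.

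**Working it through.** **Inputs**
- N = 40 (synopsis; section 9).
- At-least-VGPR rate: not given for this trial. Section 1.4.2.1 reports 47% in the phase 1b/2 study of once-weekly carfilzomib with dexamethasone, without elotuzumab. It is used here only for scale: 0.47 × 40 = 18.8, about 19 patients.
- MRD-negative count: not given. Assumed values are shown below.

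**The plan's own figure.** Section 9 gives a 95% interval of 53-83% for an expected response rate of 70% with 40 patients. The exact (Clopper-Pearson) interval for 28/40 is 53.5-83.4%, so the figure reproduces. The same method is used below. The protocol gives no calculation for MRD.

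**Relation between the two rates.** Let m be the number MRD-negative, v the number at VGPR or better, and N the number dosed. Then

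conditional rate = m/v = (m/N) ÷ (v/N).

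The conditional rate is the all-dosed rate divided by the VGPR rate. A lower VGPR rate raises it unless m falls at least in proportion.

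**Step 1: hold m = 8, so the all-dosed rate stays at 8/40 = 20.0%**

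| v | Conditional rate 8/v |
|---|---|
| 28 | 28.6% |
| 24 | 33.3% |
| 19 | 42.1% |
| 16 | 50.0% |
| 13 | 61.5% |
| 12 | 66.7% |
| 10 | 80.0% |
| 8 | 100% |

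The endpoint climbs as fewer patients respond deeply, although no more become MRD-negative.

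**Step 2: let both v and m fall (40 dosed patients per regimen)**

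| Regimen | v | m | Conditional m/v (exact 95% CI) | All-dosed m/40 (exact 95% CI) |
|---|---|---|---|---|
| A | 19 | 10 | 52.6% (28.9-75.6) | 25.0% (12.7-41.2) |
| B | 10 | 7 | 70.0% (34.8-93.3) | 17.5% (7.3-32.8) |

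B has fewer deep responders and fewer MRD-negative patients, yet it scores 70.0 − 52.6 = 17.4 points higher on the endpoint as defined. The all-dosed rate puts A first by 25.0 − 17.5 = 7.5 points. The intervals overlap widely on either measure, so the example concerns the direction in which the measure points, not a detectable difference.

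**Step 3: precision.** For m = 8 and v = 19, the conditional rate is 42.1% (20.3-66.5), an interval about 46 points wide. The all-dosed rate is 20.0% (9.1-35.6), about 27 points wide. The denominator of the conditional rate is also not known in advance.

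**The case against.** The endpoint is secondary and descriptive, is labelled as quality of response, and states its denominator openly. No test, threshold or sample size depends on it. Depth among deep responders is a legitimate estimand, and the Overview claims no more than rough comparisons with earlier reports. All of this stands, and it limits how serious the point is.

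Four stronger readings are tempting, and the protocol does not support them.

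- **That the trial cannot support any comparison on MRD.** Once the MRD-negative count and the number dosed are reported, anyone can form the all-dosed rate. The weakness lies in the headline proportion, not in the data collected.
- **That the synopsis and section 9.1 define different endpoints.** The synopsis endpoint list matches section 9.1. Only the narrative wording in the Overview refers to depth of CR, which is an editorial mismatch.
- **That every dosed patient already has an MRD status.** A patient at VGPR or better without an evaluable marrow sample has none. Treating patients below VGPR as not MRD-negative is also a convention, because Appendix 5 does not define MRD negativity.
- **That an inflated rate is to be expected here.** The counts are assumed, and the 47% comes from a regimen without elotuzumab. Holding the MRD-negative count fixed while VGPR falls is a chosen scenario.

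It can also be said that section 9.2 already analyses efficacy in all dosed patients, or that a statistical analysis plan may add an all-dosed rate. The first is a general statement and does not displace a narrower denominator written into the endpoint itself. The second is possible, but section 9.1 states its definition outright and does not leave it open.

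**Conclusion.** The point holds in a limited form. As defined in section 9.1 and the synopsis, the MRD proportion is conditioned on a treatment outcome. As a headline figure it is a poor basis for comparing regimens, because it can favour one that is worse on both VGPR and MRD negativity (70% against 53%, when the all-dosed rates are 17.5% and 25%). That a reversal is possible follows from the algebra. Its size rests on assumed counts, since the protocol gives no expected VGPR or MRD rate. The primary response-rate analysis is untouched. The change is worth making because the protocol singles this measure out for later comparison and the repair is small.

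**What to change.** In section 9.1 and the synopsis endpoint list:

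- Define the MRD endpoint as the proportion MRD-negative among all patients who received at least one dose, in line with the efficacy population in section 9.2.
- Count as not MRD-negative both patients who never reach VGPR and patients at VGPR or better without an evaluable sample. State in section 9.2 that this is an explicit exception to the rule that missing data stay missing.
- Keep the proportion among patients at VGPR or better as a supportive figure, shown with the number at VGPR or better and the number actually tested.
- Align the Overview wording about depth of CR with this definition.

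The cost is a few sentences of text and no extra sampling, because the same results yield both rates. The headline percentage will be lower, and the convention for unsampled patients is conservative. Showing the number tested lets readers judge how much that convention matters.
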